**Table 1. Visit Windows – All Variables**

Time Point	Target Day	Visit Window
Baseline (Week 0)	See Section 3.1.1 for baseline definitions	
Week 2	15	2-21
Week 4	29	22-42
Week 8	57	43-70
Week 12	85	71-98
Week 16	113	99-126
Week 20	141	127-154
Week 24	169	155-182
Week 28	197	183-210
Week 32	225	211-238
Week 36	253	239-266
Week 40	281	267-294
Week 44	309	295-322
Week 48	337	323-350
Week 52	365	351-378
Follow-up	407	379-427
Week 58		
Follow-up	449	428-469
Week 64		
Follow-up	491	470-511
Week 70		
Follow-up	533	512-553
Week 76		

**Table 2** summarises the adjusted analysis-defined visit windows for NPS and variables in which the sparsest scheduling is planned in the protocol. These variables include: WPAI, ECG, spirometry, FeNO, ACQ-6, and total IgE.

**Table 2 Visit Windows – NPS and Sparse protocol schedule**

Time Point	Target Day	Visit Window
Baseline (Week 0)	See Section 3.1.1 for baseline definitions	
Week 4	29	2-56
Week 12	85	57-126
Week 24	169	127-210
Week 36	253	211-308
Week 52	365	309-406
Follow-up	449	407-490
Week 64		
Follow-up	533	491-574
Week 76 (only NPS, ECG, spirometry, ACQ-6)		

**Table 3** summarises the visit windows which will be used for NCS and other items in the NPSD which will be summarised every two weeks (bi-weekly).

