Nasal peak inspiratory flow (NPIF)	X		X				X			X			X				X		X		X		Section 8.1.7		
Asthma/AERD/NSAID-ERD Participants Only																									
Spirometry (FEV1, FEF 25-75% and FVC)			X								X							X		X		X		Section 8.1.5	
FeNO ^h			X								X							X		X		X		Section 8.1.6	
ACQ-6			X								X							X		X		X		Section 8.1.2.5	
Nasal Polyposis Assessment																									
Nasal endoscopy/ NPS		X			X		X		X			X			X			X		X		X		Section 8.1.1	
CT Scan ^{i,t}		X																X						Section 8.1.3	
Assess decision for nasal surgery and/or SCS use	X	X	X	X	X	X	X	X	X	X	X	X	X	X	X	X ^u	X	X	X	X	X	X	Section 8.1.4		

Table 1 Schedule of Activities - Screening, Randomisation, Treatment Period, and Follow-Up

Assessment / Activity	Screening	Run-in	Randomisation	Treatment Period															EOT/ IPD	FU all ^d		Additional FU 1 st 200 participants ^c		UNS ^e	Details in CSP section or Appendix
Visit	V1	V2	V3	V4 📞 ^b	V5	V6	V7	V8	V9	V10	V11	V12	V13	V14	V15	V16	V17	V18 📞 ^b	V19	V20 📞 ^b	V21				
Week	-5	-2	0	2	4	8	12	16	20	24	28	32	36	40	44	48	52	58	64	70	76				
Visit window (days) ^a	N/A	±5	±5	±5	±5	±5	±5	±5	±5	±5	±5	±5	±5	±5	±5	±5	±5	±7	±7	±7	±7	N/A	N/A		
Laboratory Assessments																									
Clinical Chemistry	X		X		X		X		X		X		X		X		X		X		X		Section 8.2.4		
Haematology ^j	X		X		X		X		X		X		X		X		X		X		X		Section 8.2.4		
Urinalysis	X		X				X				X		X		X		X		X		X		Section 8.2.4		
Urine dipstick pregnancy test (WOCBP only)			X		X	X	X	X	X	X	X	X	X	X	X	X						Section 8.2.4.3			
Serum pregnancy test (WOCBP only)	X																X		X		X		Section 8.2.4.3		
FSH ^k	X																						Section 8.2.4.3		
Serology (HepB, HepC, HIV1, HIV2)	X																						Section 8.2.4.4		
Exploratory Assessments																									
Tezepelumab PK ^l			X		X		X		X		X		X		X		X		X		X		Section 8.5.1		

Table 1 Schedule of Activities - Screening, Randomisation, Treatment Period, and Follow-Up

Assessment / Activity	Screening	Run-in	Randomisation	Treatment Period															EOT/ IPD	FU all ^d		Additional FU 1 st 200 participants ^c		UNS ^e	Details in CSP section or Appendix
Visit	V1	V2	V3	V4 📞 ^b	V5	V6	V7	V8	V9	V10	V11	V12	V13	V14	V15	V16	V17	V18 📞 ^b	V19	V20 📞 ^b	V21				
Week	-5	-2	0	2	4	8	12	16	20	24	28	32	36	40	44	48	52	58	64	70	76				
Visit window (days) ^a	N/A	±5	±5	±5	±5	±5	±5	±5	±5	±5	±5	±5	±5	±5	±5	±5	±5	±7	±7	±7	±7	N/A	N/A		
Tezepelumab ADA/nAb ^m			X		X		X		X		X		X		X		X		X				Section 8.5.2		
Total IgE			X						X								X		X				Section 8.6.1		

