### 3.1.4 Visit Windows

All summaries and analyses, both efficacy and safety, which are presented by time point (e.g. “Week 52”) will use a visit window to classify the data record, which is derived from the assessment date relative to the reference start date. This approach allows appropriate classification of visits which may have occurred significantly earlier or later than the protocol assessment schedule, as well as the use of data captured at visits which have no fixed timing (notably the IPD visit), and the handling of data captured at visits for which the database label is incorrect and unresolvable.

Nominal database visit numbers will not be used in any summary or analysis by visit.

For Screening/run-in period, the relative day is defined as (Date of assessment – Date of randomization).

For periods after randomization:

For efficacy variables, the reference start date is the date of randomisation, and relative day is therefore defined as (Date of assessment – Date of randomisation) + 1.

For safety variables, the reference start date is the date of first dose of IP, and relative day is therefore defined as (Date of assessment – Date of first dose of IP) + 1.

Any data collected at unscheduled or repeat visits will be listed and will be included in baseline definitions (see Section 3.1.1), and in any definitions of maximum value, minimum value or last value within the relevant study period.

Data collected at unscheduled or repeat visits will also be included in visit windows, and therefore may be included in summaries or analyses by visit or used in any sensitivity analyses which involve imputation of data from participants with non-missing values to participants with missing values. In the case of a missing value at a scheduled visit, which is then followed by a non-missing value at an unscheduled or repeat assessment within the same visit window, the non-missing value at the unscheduled/repeat assessment will replace the missing value at the scheduled visit.

If a participant has more than one non-missing value within the same visit window, the following rules will apply:

- The non-missing value closest to the target day will be selected for analysis at that visit.
- If two non-missing values are equidistant from the target day, the earlier of the two values will be selected for the analysis at that visit.

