- If two non-missing values are recorded on the same day and have a different assessment time, the value with the earliest assessment time will be selected for analysis at that visit.
- If two non-missing values (for continuous variables) are recorded on the same day and have no assessment time associated with at least one of them, or the same assessment time associated with both of them, the average of the two values will be selected for analysis at that visit. For categorical variables in this situation, the worst case will be used.
- If there are multiple ADA samples in the same visit window with both positive and negative results, the sample with a positive result and the highest titre value will be selected.

If a participant has no value within a particular visit window, then the participant will have a missing value at that visit in summaries and analysis.

The same visit window definitions below will be used regardless of whether the planned treatment period or the on-treatment period is used for analysis (see Section 3.1.3). In practice, each data record in the planned treatment period will be first identified, and then further flagged according to whether it is on-treatment or off-treatment. This flag will be used to select all eligible records for subsequent visit windowing, according to whether the derived visits are to be used in a planned treatment period or an on-treatment period analysis. It should be noted that, if treatment was discontinued within a particular visit window, the rules above for handling multiple values within the same visit window could select a different record according to whether a planned treatment period analysis or an on-treatment period analysis is needed.

**Table 1** summarises the visit windows to be used for all variables unless specified otherwise. It corresponds to the full (mostly 4-weekly) protocol scheduling for clinic visits and will be

used for all variables by default, including those variables which are not capture at every clinic visit, unless indicated below that the visit windows in [Table 2](#) or [Table 3](#) should be used. Of note, Week 0 is Day 1 in the analysis following the Clinical Data Interchange Standards Consortium (CDISC) standards, although it is labelled as Day 0 in the CSP.

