**Table 3 Visit Windows – NPSD (including NCS)**

Time Point	Target Day	Visit Window
Baseline (Week 0)	See Section 3.1.1 for baseline definitions	
Week 2	15	2-15
Week 4	29	16-29
Week 6	43	30-43
...	...	...
Week 52	365	352-365
...	...	...
Follow-up	533	520-533
Week 76		

In all cases above, no time points will be presented in summary tables or included in statistical analysis which do not correspond to the time points scheduled in the protocol for the variable in question.

For CT scan, the visit window for Week 52 will include Days 1 – 490.

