#### **4.2.12 Biomarkers**

Biomarker values and change from baseline in these values will be summarised descriptively and presented graphically by treatment group up to Week 76:

- FeNO (co-morbid asthma/AERD/NSAID-ERD subset)
- Peripheral blood eosinophils (Cells/ $\mu$ L)
- Total serum IgE (IU/mL)

Analyses for the other exploratory biomarkers will be described in a separate exploratory analysis plan, which will be finalized before the database lock. These results will be reported outside the main CSR, in an addendum, or separately in a scientific report or publication.

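### SAP Table 2 gives FeNO no Week 76 window, although the protocol measures FeNO then and SAP 4.2.12 plans to report it

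*SAP*

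**What the plan says.** SAP 3.1.4 puts every by-time-point summary on date-derived windows and rules out the visit label as a substitute: "Nominal database visit numbers will not be used in any summary or analysis by visit". Table 1 is the general rule and gives way only where another table is named: "used for all variables by default, including those variables which are not capture at every clinic visit, unless indicated below that the visit windows in" (the sentence goes on to name the other two window tables). The text introducing Table 2 says that it covers NPS and the sparsely scheduled variables, and lists the latter: "These variables include: WPAI, ECG, spirometry, FeNO, ACQ-6, and total IgE". FeNO is therefore a Table 2 variable.

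The last row of Table 2 is Week 76, target Day 533, window Days 491-574. It carries the restriction "only NPS, ECG, spirometry, ACQ-6".

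SAP 4.2.12 states: "Biomarker values and change from baseline in these values will be summarised descriptively and presented graphically by treatment group up to Week 76". FeNO, in the co-morbid asthma/AERD/NSAID-ERD subset, is the first of the three biomarkers listed under that sentence. Change from baseline in FeNO is an exploratory endpoint in both documents (Protocol Section 3, SAP 1.1.5).

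In the protocol's Schedule of Activities (Table 1), FeNO has five marks: "FeNO ^h X X X X X Section 8.1.6". Spirometry and ACQ-6 have the same five.

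**The concern.** The window table and the analysis section cannot both be followed. One asks for FeNO by treatment group out to Week 76. The other closes the only Table 2 window that could hold a Week 76 FeNO value, and the bar on nominal visits removes the obvious workaround.

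The 24-week follow-up of the first 200 or so participants exists to assess durability after dosing stops. FeNO is measured twice in that follow-up, at Weeks 64 and 76. Programmed literally, the later measurement would be collected and could be listed, but it would not appear in the planned table or figure.

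**Working it through.** **1. Which windows apply to FeNO.** Table 1 is a default that gives way where Table 2 or 3 is indicated. FeNO is named for Table 2, so the Table 1 Week 76 row (Days 512-553) is not available to it.

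**2. Reproduce the Table 2 target days.** After randomisation, relative day = assessment date − randomisation date + 1, so target day = 7 × week + 1.

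| Week | 7 × week + 1 | Table 2 |
|---|---|---|
| 4 | 29 | 29 |
| 12 | 85 | 85 |
| 24 | 169 | 169 |
| 36 | 253 | 253 |
| 52 | 365 | 365 |
| 64 | 449 | 449 |
| 76 | 533 | 533 |

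All seven agree.

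**3. Place a Visit 21 FeNO value.** The protocol allows ±7 days at Visit 21: 533 − 7 = 526 and 533 + 7 = 540. Days 526-540 lie wholly inside 491-574, the row closed to FeNO. They lie wholly outside 407-490, the Week 64 row, which is the last one open to it. No FeNO window captures the value.

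**4. Confirm that FeNO is scheduled at Visit 21.** In the machine-read text of the Schedule of Activities, the FeNO, spirometry and ACQ-6 rows have marks in identical positions (3, 11, 18, 20, 22). These rows carry one cell more than the NPIF row, whose marks are at 1, 3, 7, 10, 13, 17, 19 and 21. The NPIF positions match the visits written out in Protocol 8.1.7, so that row is intact. Removing the extra cell after Visit 3 puts the FeNO marks at Visits 3, 10, 17, 19 and 21, that is Weeks 0, 24, 52, 64 and 76. Read without this correction, two marks would fall on Visits 18 and 20, which are telephone visits where FeNO cannot be measured. The SAP also gives spirometry and ACQ-6, which share the FeNO pattern, a Week 76 window.

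**5. Compare the Week 76 list with the schedule.**

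| Table 2 variable | Scheduled at Visit 21 | In the Week 76 list |
|---|---|---|
| NPS | yes | yes |
| ECG | yes | yes |
| Spirometry | yes | yes |
| ACQ-6 | yes | yes |
| FeNO | yes | **no** |
| WPAI | no | no |
| Total IgE | no | no |

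The list follows the schedule for every variable except FeNO.

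**6. Size.** About 200 participants are to be followed to Week 76 (Protocol 4.1), and 50%-70% of the study population is to have co-morbid asthma/AERD/NSAID-ERD, the only group with FeNO measurements. 200 × 0.50 = 100 and 200 × 0.70 = 140.

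**The case against.** **The Week 76 horizon in 4.2.12 may be generic.** One lead-in sentence covers FeNO, eosinophils and total IgE, and total IgE is not collected at Week 76. For at least one biomarker, Week 76 is thus an outer limit and not a promise of a data point. That is fair as far as it goes. However, the rule below Table 3 settles such cases: it removes from tables and analyses only those time points "included in statistical analysis which do not correspond to the time points scheduled in the protocol for the variable in question". It takes out Week 76 for total IgE. It does not take out Week 76 for FeNO, which is scheduled then.

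**A programmer might fall back on Table 1,** whose Week 76 row contains Days 526-540. That reading would rescue the data, but it conflicts with FeNO being named for Table 2. It would also mean using two window tables for one variable, which the SAP does not provide for.

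**The Visit 21 mark is inferred from a displaced table row.** Protocol 8.1.6 names no weeks for FeNO and only points to the schedule. The realignment in step 4 is therefore an inference. It is supported by the NPIF row, by the telephone visits and by the SAP's own treatment of spirometry and ACQ-6.

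**The consequence is modest.** This stands. The Week 64 FeNO value keeps its window. With the last dose at Week 48 it comes 64 − 48 = 16 weeks after dosing, an interval that Protocol 8.3.12.2 equates with five half-lives. Off-treatment FeNO information therefore survives. What is lost is the second and later point, 76 − 52 = 24 weeks after end of treatment.

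**Conclusion.** The concern holds. Followed literally, the SAP collects Week 76 FeNO, plans to show it, and gives it no analysis visit. No reason for leaving it out is given, and the match between the Week 76 list and the schedule for every other Table 2 variable points to an oversight.

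The loss is one of five scheduled FeNO time points and one of two in off-treatment follow-up, for up to about 100-140 participants. That range assumes that the study-wide 50%-70% target also holds among the first 200 or so randomised, which the documents do not state. It is a ceiling before dropout and missed measurements.

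The finding is minor. FeNO is an exploratory endpoint summarised descriptively in a subset. The co-primary and key secondary endpoints, the multiplicity procedure and power are unaffected, and the values can still be listed.

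**What to change.** In SAP Table 2, add FeNO to the variables allowed in the Week 76 row, so that it covers NPS, ECG, spirometry, FeNO and ACQ-6. Every in-window Visit 21 FeNO value (Days 526-540) then falls within Days 491-574 and enters the output planned in 4.2.12. The cost is one word, with no effect on any other analysis.

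If Week 76 FeNO is deliberately not wanted, limit FeNO in 4.2.12 to Week 64 and give the reason. That also removes the contradiction, but it leaves collected data unused.

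SAP 2.1.4 says the SAP will not be updated after primary database lock. If the lock has already passed, record the corrected window in the clinical study report instead.

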**Table 3 Visit Windows – NPSD (including NCS)**

Time Point	Target Day	Visit Window
Baseline (Week 0)	See Section 3.1.1 for baseline definitions	
Week 2	15	2-15
Week 4	29	16-29
Week 6	43	30-43
...	...	...
Week 52	365	352-365
...	...	...
Follow-up	533	520-533
Week 76		

In all cases above, no time points will be presented in summary tables or included in statistical analysis which do not correspond to the time points scheduled in the protocol for the variable in question.

For CT scan, the visit window for Week 52 will include Days 1 – 490.

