At Week 0, the Health Care Professional (HCP) will administer the study drug. Optional home IP administration by HCP can take place only at Week 16, Week 20, Week 28, Week 32, Week 40, Week 44, and Week 48. The rest of the IP administration visits must occur at the study centre.

Participants will be evaluated for efficacy, safety, pharmacokinetics (PK), ADA, and sample collection of blood and nasal lining fluid for exploratory biomarkers will be performed

throughout the study. If at any point a participant meets IP discontinuation (IPD) criteria, an early IPD Visit will be performed (see Section 7.1).

At selected clinical sites, the participants may consent optionally to the nasal biopsy sub-study for up to approximately 60 participants. The target number will also be monitored closely throughout the study. A baseline nasal biopsy will be obtained prior to randomisation, at V2. The nasal biopsy at V2 must be performed prior to nasal endoscopy. Another biopsy of nasal polyp tissue will be obtained at EOT visit at V17 (Week 52) (see Section 8.6). The EOT nasal biopsy must be obtained after nasal endoscopy has been performed. Additionally, as part of the sub-study, nasal lining fluid will be collected at Visit 2 and a blood sample to assess Staph A enterotoxin-specific IgE status will be collected at Visit 3 and EOT/IPD.

CT scans will be performed for all participants. A baseline CT scan will be done between V2 and V3 (after ensuring the participant has met inclusion/exclusion criteria, including NPS score by central reader) and a post-baseline CT scan at EOT/IPD (V17/Week 52). CT scan is required before first NP surgery and/or initiation of first course of SCS treatment for NP (see Section 8.1.3).

An independent adjudication committee will be constituted to provide an external independent assessment of blinded data during the study to confirm the diagnosis of major adverse cardiac events (MACE) (to be defined in the charter) and investigator-reported malignancies that occur from randomisation until the end of the follow-up period; please refer to Section 8.3.9.

4.1.1 Study Conduct Mitigation During Study Disruptions Due to Cases of Civil Crisis, Natural Disaster, or Public Health Crisis

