## 3 PRIMARY AND SECONDARY VARIABLES

### 3.1 General Definitions

#### 3.1.1 Definition of Baseline

In general, the last non-missing measurement on or prior to the date of randomisation will serve as the baseline measurement for efficacy variables. If there is no value on or prior to the date of randomisation, then the baseline value will be set to missing.

In general, the last non-missing measurement prior to first dose of study treatment will serve as the baseline measurement for safety variables. If there is no value prior to first dose of study treatment, then the baseline value will be set to missing.

Where unscheduled/repeat assessments are relevant and exist for any participant at a particular visit specified below, they will also be considered in the baseline definitions, provided they remain prior to the date of randomisation (efficacy) or the date of first dose of study treatment (safety).

For the NPSD (NCS included), the baseline is the average of daily responses from Day -13 to Day 0. The mean is calculated as the sum of all non-missing daily scores over these 14 sequential days divided by the number of non-missing daily scores. If more than 7 daily scores (>50%) within the baseline period are missing, then baseline is set to missing.

Of note, Day 0 is Day 1 in the analysis following the Clinical Data Interchange Standards Consortium (CDISC) standards (Section 3.1.4), although it is labelled as Day 0 in the CSP.

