#### 4.2.6 Co-Primary Endpoints

##### 4.2.6.1 Primary Estimand Analysis

For the primary estimand the primary analysis of the co-primary efficacy endpoints (mean change from baseline in NPS at 52 weeks and mean change from baseline in NCS at 52 weeks) uses a composite variable strategy in which data collected after nasal polyp surgery will be replaced with the worst possible score (WPS). Data collected after SCS for NP will be replaced with the worst post-baseline observation prior to the SCS for NP (WOCF). Data collected after treatment discontinuation without surgery or SCS for NP will be included in the analysis. For participants whose post-baseline data are all missing, the baseline value will be used in the place of WOCF. For participants who discontinue the study without NP surgery or SCS/biologic for NP, a multiple imputation (MI) approach will be used to impute missing Week 52 value assuming missing at random (MAR). A random seed of 539612 will be used for both monotone and non-monotone imputations.

Of note, biologics are prohibited medications per the CSP Section 6.4. However, if biologics are used for NP, the same strategy used for the SCS for NP will be applied.

The following steps will be taken to generate completed datasets up to Week 52 for analysis:

**Step 1:** Data collected after date of surgery, SCS for NP, or biologic for NP treatment will be set to missing for the purpose of imputation. For the NCS, if the intercurrent event occurred prior to the last day of a bi-weekly interval, the bi-weekly mean NCS for that period and all periods afterwards will be set to missing.

**Step 2:** Based on the dataset from Step 1, the intermittent missing data will be imputed using the MCMC method in SAS PROC MI with an IMPUTE=MONOTONE statement for each treatment group separately. The imputation model will include baseline co-morbid asthma/AERD/NSAID-ERD status, prior surgery status, region, baseline value, and data at each timepoint. 100 imputed datasets will be generated.

**Step 3:** The remaining monotone missing data will be imputed using the MI procedure with the ‘MONOTONE REG’ option for each treatment group separately. The imputation model will include baseline co-morbid asthma/AERD/NSAID-ERD status, prior surgery status, region, baseline value, and data at each timepoint.

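### The Week 52 CT window opens on the randomisation date, and Step 4 does not clearly give the worst possible score to a pre-surgery record windowed to Week 52

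*SAP*

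**What the plan says.** **Window and baseline.** Below Table 3, SAP Section 3.1.4 says: "For CT scan, the visit window for Week 52 will include Days 1 – 490". For efficacy after randomisation, the "relative day is therefore defined as (Date of assessment – Date of randomisation) + 1", so the randomisation date is Day 1. Section 3.1.3 ends screening the day before, so a scan on the randomisation date takes this formula. Section 3.1.1 says that "the last non-missing measurement on or prior to the date of randomisation will serve as the baseline measurement for efficacy variables". When a window holds several records, "The non-missing value closest to the target day will be selected for analysis at that visit"; for Week 52 the target is Day 365. The first post-baseline windows in Tables 1, 2 and 3 all begin at Day 2.

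**When CT is done.** Protocol Section 4.1: "A baseline CT scan will be done between V2 and V3", V3 being the randomisation visit. Protocol Sections 7.1.1 and 8.1.3 place a CT before a first polyp surgery. The discontinuation-visit CT is done only if 12 weeks have passed since the baseline scan. After discontinuation for surgery, no further CT or endoscopy is required.

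**Analysis.** SAP Section 4.2.7.1.3 sends LMK to the methods of Sections 4.2.6.1 and 4.2.6.2. There, Step 1 blanks data collected after surgery (and, under the primary estimand, after systemic steroids or a biologic for polyps). Steps 2 and 3 impute. Step 4 replaces post-surgery scores with the worst possible score (WPS) and, under the primary estimand, post-steroid and post-biologic scores with the worst observation carried forward (WOCF). Section 4.1.3.1 names the WPS for NPS (8) and NCS (3) only. The end of Section 4.1.3.3 extends the strategies to the secondary endpoints, and Section 3.3.4 gives the LMK maximum as 24.

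**The concern.** LMK is one of the four endpoints in the truncated Holm family, and NPS is co-primary. Two of the rules, followed literally, can give a wrong Week 52 value.

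(a) One scan can be both baseline and Week 52. The change is then 0 by construction, where Section 4.2.6.1 would treat Week 52 as missing and impute it.

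(b) A participant who has surgery usually leaves a pre-surgery scan as the only post-baseline CT, and the 490-day window labels it Week 52. Step 1 leaves it alone because it predates surgery. Step 4 speaks of post-surgery scores without saying whether the date of the record or the analysis time point decides. A program keyed to record dates would keep a pre-surgery LMK for someone whom the composite strategy counts as a poor outcome. An NPS endoscopy on or after Day 309 followed by surgery before Week 52 is exposed in the same way. Only NCS has an explicit rule for an event inside its interval.

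What is at stake is whether the estimate matches its estimand and whether two programmers would get the same number.

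**Working it through.** **The plan's own figures.** LMK: SE = 5.45 × √(2/200) = 0.545, and 5/0.545 = 9.17, so power at two-sided 1% is above 99.99% (43 per arm would give 95%). The stated floor of at least 95% holds. Surgery decision: placebo 11%; tezepelumab 1 − 0.89^0.33 = 3.8%; about 29.5 events; Schoenfeld power 85% at 5%, in line with the stated 80% or more.

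**Day 1.** Day 1 lies 364 days from target; Day 2 lies 363 and Day 490 lies 125. Any scan on Days 2–490 therefore beats a Day 1 scan. The fault needs a baseline CT on the randomisation date and no other scan through Day 490. The change is then baseline minus itself, 0.

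**Surgery, by record type**

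| Record | Window | Step 1 | Step 4 by record date | Step 4 by time point |
|---|---|---|---|---|
| Pre-surgery CT, no later CT | Week 52 (Days 1–490) | kept | pre-surgery LMK stays | 24 |
| Pre-surgery endoscopy, Day 309 or later | Week 52 (Days 309–406) | kept | pre-surgery NPS stays | 8 |
| Pre-surgery endoscopy before Day 309, none later | earlier visit | Week 52 missing, so imputed | imputed value has no record date | 8 |

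The columns disagree in the first two rows. For LMK the first row is the normal surgery case.

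**Illustration for LMK, record-date reading.** The documents do not give the pre-surgery LMK (L) or the rate of actual surgery. Assume L = 12 to 22, use the planning decision rates in place of actual surgery, and take a constant hazard.

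- Arm difference in rates: 0.1100 − 0.0377 = 0.0723. Loss of effect = 0.0723 × (24 − L): 0.87 points at L = 12, 0.43 at 18, 0.14 at 22.
- Surgeries after Week 12 only, since earlier ones normally yield no discontinuation-visit CT: 0.0835 − 0.0289 = 0.0546, giving 0.65 (L = 12) to 0.11 (L = 22).
- If only half of those decisions become surgery by Week 52 (assumed): 0.33 to 0.05.
- Largest case: (5 − 0.87)/0.545 = 7.58 standard errors; power at 1% is still above 99.99%.

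**Illustration for NPS.** Surgeries in Weeks 44–52 (about Days 309–365): 0.0161 placebo (3.2 of 200) and 0.0057 tezepelumab (1.1 of 200), difference 0.0104. With a pre-surgery NPS of at least 5 (assumed), the shift is at most 0.0104 × (8 − 5) = 0.03 points against a planned 1.8. It is smaller if some of those endoscopies fall before Day 309.

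**The case against.** The intent is not really in doubt. Section 3.1.2 takes change from a post-baseline value, and a scan already serving as baseline is not one. CT is listed at V2, and the suggested V3 order of assessments contains none. Step 4 acts on imputed datasets in which filled cells have no collection date, so for them it can only work by time point. The SNOT-22 responder rule in Section 4.2.7.2.1 also judges events at or before the time point. The LMK worst score of 24 follows from Sections 3.3.4 and 4.1.3.3.

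Most of this stands as evidence of what was meant. It does not close the gaps: no rule removes a Day 1 baseline scan from the window, and nothing in Step 4 covers an observed pre-surgery record carrying the Week 52 label. The SAP settles the within-interval problem for NCS and leaves it open for LMK and NPS.

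A reader might also infer that a lone scan from an early discontinuation visit is an undeclared carry-forward needing its own LMK sensitivity analysis. The documents do not support that charge. Section 3.1.4 gives the use of discontinuation-visit data as a purpose of windowing, and Protocol Section 4.1 describes a single post-baseline CT time point at end of treatment or discontinuation. Follow-up options 1 and 2 bring a Week 52 CT, which the closest-to-target rule would select. An extra analysis is a preference. Under the US FDA estimand, a pre-steroid scan could fill Week 52 only if the scheduled post-steroid scan is missing, and no rate is given for that.

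**Conclusion.** Two minor defects stand. The CT window opens one day too early, which matters only for a same-day baseline scan with no other scan to Day 490. Step 4 is ambiguous for an observed pre-surgery record labelled Week 52: the usual surgery case for LMK, and a small late subset for NPS. Both can yield a wrong Week 52 value if the text is followed literally, so they are more than missing detail, although the intended reading can be recovered.

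The Day 1 fault cannot be sized, because the documents give no rate of same-day baseline scans or of missing later scans. For the surgery fault the direction is clear under the planning rates: more surgery on placebo means that keeping pre-surgery scores shrinks the tezepelumab effect on LMK. A reader might infer a bias towards tezepelumab or a threat to LMK significance; the planning figures support neither. Nor should the illustrative shifts be quoted as a percentage loss of effect. They assume a reading the plan probably did not intend, decision rates in place of actual surgery, and pre-surgery scores that are not documented.

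**What to change.** In Section 3.1.4, start the CT Week 52 window at Day 2 and exclude any scan used as baseline.

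In Step 4 of Section 4.2.6.1, and in its use under Section 4.2.6.2, add for LMK and NPS: if surgery, or the steroid or biologic event where the estimand calls for replacement, falls on or before the participant's Week 52 visit (Day 365 if there is no visit), the Week 52 value is set to WPS or WOCF as that estimand requires, whatever the date of the windowed record. State WPS = 24 for LMK.

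The cost is one bound and a sentence or two. No observed scan is lost except as a duplicate of baseline, and no new data or analysis is needed. Section 2.1.4 bars SAP updates after primary database lock, so the change belongs before lock; failing that, the clinical study report should state which rule was programmed.
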